#### **Statical Analysis Plan**

#### Sample Size, Randomization and Formation of Groups

A power analysis was conducted to determine the number of participants to be included in the study. In order to exceed the 80% power level, it was determined that the study should be conducted with 50 individuals (25 participants in the training and 25 participants in the control group), at a significance level was set at 5% with an effect size of 0.518 (df=41; t=1.683) [1].

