Cover Page for Study Protocol and Informed Voluntary Consent Form

Principal Investigator Name:	[name]
NCT Number:	Not yet
Official Title of Study:	Effects of Carbohydrate Counting Training Versus Standard
	Nutritional and Medical Therapy on Glycemic Control and
	Sarcopenia in Type 2 Diabetes: A Randomized Controlled
	Trial
Document Date:	March 24, 2022

Study Protocol

The Aim of the Study

The aim of this study to evaluate the effects of advanced carbohydrate counting training on anthropometric/body composition, biochemical, and clinical parameters of patients with type 2 diabetes mellitus who receive intensive insulin therapy. In addition, this study also evaluated the sarcopenia status of the patients and the effect of carbohydrate counting training on sarcopenia.

Study Design and Participants:

This study was planned as a randomized, controlled, 24-week study and was conducted with the voluntary participation of individuals with type 2 diabetes who were treated with intensive insulin. The study sample consisted of patients who received outpatient treatment at the Uskudar Diabetes Polyclinic of the Fatih Sultan Mehmet Training and Research Hospital Additional Service Building of the Ministry of Health of the Republic of Turkey between August 2022 and December 2024.

Inclusion criteria included, a history of type 2 diabetes mellitus or using insulin for more than one year, being over 18 years old, receiving basal and bolus insulin treatment, not having received carbohydrate counting training before, not receiving treatment with sulfanylurea drugs from oral anti-diabetics. Exclusion criteria included being pregnant or breastfeeding or planning a pregnancy during the study period, discontinuing insulin treatment during the study period, having active proliferative retinopathy, severe nephropathy, severe or newly diagnosed cardiac disease within 6 months or stage III–IV heart failure, having dementia or psychosis and cognitive impairment, receiving glucocorticoid treatment, being fed enterally or parenterally and receiving nutrition treatment due to another/concomitant disease, having end-stage renal or hepatic/ renal disease (other than proteinuria); having liver disease/microangiopathy diseases, having clinical cancer, chronic respiratory disease or amputations, or having any disease or condition that would prevent completion of the study.

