The participants' hand grip strength was measured three times with a digital hand dynamometer (CAMRY-EH101, USA) and the mean value in kg was calculated. In addition, the threshold values determined for hand grip strength in the European Working Group on Sarcopenia in Older People guideline are 15 kg for women and 20 kg for men [2]. In this context, individuals below this threshold value were evaluated as low muscle strength. Skeletal muscle mass data obtained from the BIA measurement results and skeletal muscle according to the height obtained from this data were calculated by dividing the skeletal muscle mass by the square of the height. In this context, in the European Working Group on Sarcopenia in Older People guideline, the threshold values for evaluation within the scope of sarcopenia were determined as 15 kg for women and 20 kg for men for skeletal muscle, while 5.5 kg/m2 for women and 7 kg/m2 for men for skeletal muscle by height [2]. In this context, individuals below this threshold value were evaluated as having low muscle mass.

In the timed walk-up test, the patient is asked to get up from the chair, walk at a normal walking speed on a flat surface of 3 meters, turn around, walk back and sit back in the chair [3]. The time between the patient getting up from the chair, walking and sitting down again is recorded and the patient's dynamic balance during walking is also evaluated. In addition, the threshold value of the test duration in the evaluation of sarcopenia was determined as 10.85 s in the study by Christopher et al. and individuals above this threshold value were evaluated as low physical performance [4].

Blood pressure of the participants was measured with an automatic sphygmomanometer (SCIAN LD-533, Germany). Three repeated measurements were made on the right arm in the sitting position with the arm at the level of the heart and after a rest period of at least 10 minutes and the mean was calculated. In addition, a 24-hour retrospective food consumption record was applied to evaluate the energy and nutrient intakes. The calculation of the energy, macro and micro-nutrient intakes of the participants was carried out using the Turkish Nutrition Database Ebispro for Windows program (version 7.2) [5].

Reference

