### **Statistical Analyses**

The statistical analysis of the data obtained from the study was evaluated using the IBM SPSS Statistics (version 22.0) package program. In order to evaluate the suitability of the data for normal distribution, One-Sample Kolmogorov-Smirnov test was conducted and kurtosis and skewness of the data was evaluated. Independent sample t-test was used to compare two independent groups among with normal distribution, dependent sample t-test and mixed design ANOVA were used to compare repeated measurements between two independent groups. All data have been provided with mean  $\pm$  standard deviation (mean $\pm$ SD). Mann-Whitney U test was used to compare data not showing normal distribution, and Wilcoxon test and Friedman test were used for repeated measurements between two groups. Categorical variables were compared using chi-square test and Fisher's exact chi-square test, and these data were shown with frequency (n, %) values. The significance level between the data was accepted as p=0.05. The graphical representations of the data were evaluated using the GraphPad Prism (version 9.3.0) package program.

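### Arm comparisons of muscle mass and grip strength include no sex term, although the protocol's own cut-offs for these measures differ by sex; adding one costs a single degree of freedom

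*SAP*

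**What the plan says.** - **Design.** Protocol, Study Design and Participants: "This study was planned as a randomized, controlled, 24-week study".
- **Sample size and allocation.** The SAP section headed "Sample Size, Randomization and Formation of Groups" contains the power analysis and the split into "25 participants in the training and 25 participants in the control group". It gives no method of generating the sequence, no concealment, and no blocking or stratification.
- **Sex-specific thresholds.** Protocol, Evaluation: low grip strength is below 15 kg in women and 20 kg in men. Skeletal muscle mass has the same pair of values. The height-adjusted index uses "5.5 kg/m2 for women and 7 kg/m2 for men for skeletal muscle by height". The timed walking test has one threshold, 10.85 s, for both sexes.
- **Timing.** Body composition and grip strength are measured at baseline, week 12 and week 24.
- **Analysis.** SAP, Statistical Analyses: "Independent sample t-test was used to compare two independent groups" where data are normally distributed, with a Mann-Whitney test otherwise. A mixed-design ANOVA handles repeated measurements, and chi-square or Fisher tests handle categories. No analysis names sex as a factor or covariate, and the SAP does not say which comparison decides the result.

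**The concern.** Sarcopenia is in the trial's title. By setting separate thresholds, the Protocol treats grip strength and skeletal muscle as measures whose normal level depends on sex. A pooled comparison of visit values then has two sources of spread: patients differing within a sex, and the gap between the sexes. The second is known, recorded and removable, but the plan leaves it in the error term.

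Two things are at stake. The first is precision: a real training effect on muscle or strength is harder to detect. The second is interpretation: with 25 per arm the numbers of women can differ noticeably by chance, and a reader of an unadjusted week-24 difference in muscle mass cannot tell how much of it reflects the sex mix.

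**Working it through.** **1. The plan's own figure.** The inputs are an effect size of 0.518, 25 per arm and a 5% level (SAP, sample size section). For a two-group t-test the noncentrality is 0.518 × √(25/2) = 1.831. With 48 degrees of freedom and a two-sided critical value of 2.011, power is 43% (56% one-sided). The stated aim, "In order to exceed the 80% power level", is therefore not reproduced for a two-group comparison. That is a separate matter. Here 43% serves only as the unadjusted starting point, and 0.518 only as a reference effect, because the SAP does not name the outcome behind it.

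**2. Variance left in by pooling.** Let D be the sex gap in within-sex SDs and p the share of women. Then total variance / within-sex variance = 1 + p(1 − p)D². The documents give neither D nor p. Assume p = 0.5 and D from 1 to 2.

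**3. Power with sex in the model.** An effect of 0.518 pooled SD equals 0.518 × √(1 + D²/4) within-sex SDs. The noncentrality is that value × √12.5, with 47 degrees of freedom and a critical value of 2.012.

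| D (assumed) | Variance ratio | Effect in within-sex SDs | Noncentrality | Two-sided power |
|---|---|---|---|---|
| Sex ignored | – | – | 1.831 | 43% |
| 1 | 1.25 | 0.579 | 2.048 | 52% |
| 1.5 | 1.56 | 0.648 | 2.289 | 61% |
| 2 | 2.00 | 0.733 | 2.590 | 72% |

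These figures take the sexes as evenly split between arms. Without stratification, the difference between arms in the share of women has an SD of 0.143. The average loss of information is therefore about 0.143² = 2%, which barely changes the table.

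**4. How large chance imbalance is.** With 25 women among 50 patients and an unstratified 25/25 split (hypergeometric), the share of women differs by 20 points or more, for example 15 against 10, in 26% of trials. With 20 or 30 women it is 15%. A 20-point difference shifts the arm difference by 0.20 × D / √(1 + D²/4): 0.20/1.118 = 0.18 pooled SD at D = 1, and 0.40/1.414 = 0.28 at D = 2. The standard error of the arm difference is √(2/25) = 0.283 SD, so such a shift is no larger than one standard error.

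**5. Does this inflate false positives?** No. The pooled SD contains the between-sex spread, so the t-test already allows for it. Simulation with no treatment effect (25 women of 50, assumed sex gap 12-16 kg, within-sex SD 5-6 kg, 20,000 runs per setting) rejected in 4.9-5.2% of runs.

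**6. Which analyses are affected.** A sex difference that is constant over time drops out of each patient's change, and so out of the group-by-time term. It remains in t-tests and Mann-Whitney tests at week 12 or 24 and in the group main effect of the mixed ANOVA.

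**The case against.** The strongest reply is that the planned analysis already deals with much of this. The mixed ANOVA uses the baseline values, and its group-by-time term is free of a stable sex difference. If that term decides the result, adding sex as a main effect gains little. The low-strength and low-muscle categories use sex-specific thresholds, so sex is partly accounted for there too. This stands, and it confines the point to visit values and the group main effect. It does not remove the point, because the SAP lists independent-group tests alongside the ANOVA and ranks neither.

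A reader might go further in three ways that the documents do not support.

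- **That chance imbalance could mimic more than half the planned effect.** Half of 0.518 is 0.259 SD. With half women, a shift that large has a probability of about 2%, 9% and 26% for assumed D of 1, 1.5 and 2. It is also random error already in the standard error, not bias, and nothing links 0.518 to muscle mass.
- **That the outcomes in general depend on sex.** The Protocol gives sex-specific cut-offs only for grip strength and skeletal muscle. It gives none for waist or fat mass, and nothing shows such dependence for HbA1c, glucose or lipids.
- **That allocation was unconcealed or predictable.** The reviewed text is silent on the method, and part of the SAP was not available for review. The 25 + 25 split is a sample-size result, not a stated cap or allocation rule.

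**Conclusion.** The point holds as a missed gain in precision on muscle mass, muscle by height and grip strength. It is not a source of bias or of false positives. For an effect of 0.518 pooled SD at 25 per arm, two-sided power rises from 43% to about 52% with an assumed sex gap of 1 within-sex SD, 61% at 1.5 and 72% at 2, with half the patients women. The gain shrinks towards nothing as the gap does, and it does not apply to change scores or the group-by-time term. The actual gap and share of women are not in the documents, so the size is conditional on these assumptions.

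The undescribed randomization method is a reporting gap. Because the training sessions cannot be blinded to patients or trainers, readers will want it filled, but it is not evidence of a flawed allocation.

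**What to change.** In the SAP's Statistical Analyses section, include sex as a factor in the arm comparisons of muscle mass, muscle by height and grip strength. For week-12 and week-24 values, replace the pooled t-test with a linear model containing arm and sex. In the mixed ANOVA, add sex as a between-subject main effect, without an arm-by-sex interaction.

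The cost is one degree of freedom (48 to 47), which moves the critical value only from 2.011 to 2.012. No patients, visits or measurements are added, because sex must already be recorded to apply the cut-offs.

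Under the heading that announces randomization, state how the sequence was generated, who held it and how it was concealed until assignment. Sex-stratified allocation is a reasonable option but not a requirement. The Protocol describes the study in the past tense, so stratification may no longer be possible, whereas the sex factor and the description of the method can still be added.

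### 25 patients per arm do not give more than 80% power at effect size 0.518 in the two-arm t-test (about 43% two-sided, 56% one-sided), and df=41 does not fit 25 + 25

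*SAP*

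**What the plan says.** The Protocol (Study Design and Participants) describes a two-arm comparison: "This study was planned as a randomized, controlled, 24-week study".

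The SAP (Sample Size, Randomization and Formation of Groups) justifies the size of the trial in one sentence: "In order to exceed the 80% power level, it was determined that the study should be conducted with 50 individuals", split 25 and 25, "at a significance level was set at 5% with an effect size of 0.518 (df=41; t=1.683". It cites one earlier trial as its source. It does not name the outcome behind 0.518, the kind of effect size, the test, the number of sides or any allowance for dropout.

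The SAP (Statistical Analyses) says of normally distributed data: "Independent sample t-test was used to compare two independent groups". It assigns the dependent-samples t-test and mixed-design ANOVA to repeated measurements. On the level of the tests it says only "The significance level between the data was accepted as p=0.05", again without giving the number of sides.

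**The concern.** An effect size near 0.5 with 25 per arm is well short of 80% power in an ordinary two-sample t-test, so the claim looked wrong on sight. The degrees of freedom raised a second doubt. Two arms of 25 give 48, not 41, so the quoted t cannot be the critical value for the stated sample.

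This is the SAP's only justification of the sample size. A reader who accepts it will assume that a true difference of 0.518 SD would be missed less than 20% of the time. If the real risk is around one half, a non-significant difference between the arms may be read as evidence that training does nothing, when the trial could not settle the question.

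**Working it through.** **Inputs.** From the SAP's sample-size paragraph: effect size 0.518, level 5%, 25 per arm, target power above 80%, df=41, t=1.683. From its Statistical Analyses section: independent-samples t-test between groups. The number of sides is not given, so both are shown.

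**1. The plan's claim, using the between-group test it names.** For a two-sample t-test:

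- df = n1 + n2 − 2 = 25 + 25 − 2 = 48
- noncentrality = d × √(n1·n2/(n1 + n2)) = 0.518 × √(625/50) = 0.518 × √12.5 = 1.831
- power = probability that a noncentral t with these parameters falls beyond the critical value

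| Sides | Critical t, df=48 | Power |
|---|---|---|
| Two | 2.011 | 43.4% |
| One | 1.677 | 56.4% |

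A simulation of 200,000 trials gave 43.6% and 56.4%. The claim of more than 80% does not reproduce on either choice of sides.

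**2. The printed df and t.** At 41 df the 5% critical value is 1.683 one-sided and 2.020 two-sided, so the printed pair is a one-sided value at 41 df. It does not match 48 df (1.677 or 2.011). If df=41 meant 43 patients in two arms (21 + 22), the noncentrality is 0.518 × √(462/43) = 1.698 and power falls to 38.2% two-sided or 51.0% one-sided.

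**3. A calculation that fits parts of the text.** For a one-sided one-sample or paired t-test, df = n − 1 and noncentrality = 0.518 × √n:

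| n | df | Power, one-sided |
|---|---|---|
| 24 | 23 | 79.3% |
| 25 | 24 | 80.8% |
| 41 | 40 | 94.7% |
| 42 | 41 | 95.1% |

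So 25 is the smallest n reaching 80%. The smallest n reaching 95% is 42, where df=41 and t=1.683. No single set-up tried yields 25 + 25, df=41 and t=1.683 together. Two-sided, the paired test at n=25 has 70.0% power.

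**4. Other readings of 0.518.**

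- *Cohen's f.* Then d = 2 × 0.518 = 1.036, and two-sided power with 25 per arm is 94.8%. But 16 per arm would already give 80.9%, and the reading does not produce the quoted t.
- *Mixed-ANOVA interaction with f = 0.518/2 = 0.259.* Power is 85.8% to over 99% for two or three measurements and an assumed correlation of 0.3 to 0.7. With two measurements, a difference in change of δ SD moves each cell by ±δ/4, so f = δ/4. An f of 0.259 therefore means δ = 1.036 SD, twice the effect in step 1.
- *Change score with a true difference of 0.518 SD, two-sided.* Power is 43.4%, 51.9%, 63.9% and 81.0% at assumed baseline-to-follow-up correlations of 0.5, 0.6, 0.7 and 0.8.
- *Baseline-adjusted analysis (ANCOVA), same effect and correlations.* Power is 54.5%, 61.2%, 71.0% and 84.9% two-sided; 67.0%, 73.0%, 81.1% and 91.4% one-sided.

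**5. What 25 per arm can do in the two-sample t-test.**

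- 80% power is reached at d=0.81 two-sided or 0.71 one-sided.
- For scale, 80% power at d=0.518 needs 60 per arm two-sided (80.3%; 59 gives 79.7%) or 47 one-sided (80.2%; 46 gives 79.4%).
- An observed difference of exactly 0.518 SD gives t(48) = 1.83, with p=0.073 two-sided and p=0.037 one-sided. The 95% interval is 0.518 ± 2.011 × √(2/25) = 0.518 ± 0.569, about −0.05 to 1.09 SD.

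**The case against.** The power shortfall depends on a reading that the SAP does not spell out. The sample-size paragraph names neither a test nor a type of effect size, and no sentence ties it to the independent-samples t-test. Patients are measured three times and mixed ANOVA is among the named analyses, so 0.518 could be something other than a between-arm d. As Cohen's f it gives 94.8%, and nothing says that 25 was meant as the minimum, so the fact that 16 would do is not a contradiction. A one-sided paired test does give 80.8% at n=25, in which case the fault is the choice of test, not the arithmetic. The only evidence on sides, t=1.683, points to a one-sided test, where an observed 0.518 SD would be significant. The link from df=41 to 95% power at n=42 is conjecture, because the SAP mentions no 95% target.

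Much of this stands as a limit on what can be said. The 43% and 56% hold for a between-arm d in a two-sample t-test, and the paired origin is an inference. It does not rescue the paragraph. The readings that put the two-arm comparison above 80% rest on an effect-size type or a correlation that the SAP does not give, and the F-test readings would not report t=1.683. The paired reading powers change within one arm, not the randomised comparison. The clash between df=41 and 25 + 25 remains however 0.518 is read.

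**Conclusion.** The concern holds. For the named between-group t-test with 25 per arm and d=0.518, power is 43.4% two-sided or 56.4% one-sided, which is 37 or 24 percentage points below the 80% claimed. The chance of missing an effect of that size is about 57% or 44%, not under 20%. This assumes that 0.518 is a standardised difference between arms and that the analysis does not adjust for baseline.

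Separately, and without that assumption, the quoted df and t do not belong to a two-sample t-test on 25 + 25. The justification cannot be reproduced as written. Whether the cited trial supports 0.518 cannot be judged from these documents.

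**What to change.** In the SAP's sample-size paragraph:

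1. State the test, the number of sides, the type of effect size, and the outcome and figure in the cited trial from which 0.518 was actually taken. Do not attach 0.518 to an outcome that the source does not support.
2. Replace the power claim with:

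> With 25 per arm, a two-sample t-test at the 5% level has 43% power two-sided (56% one-sided) at d=0.518, and 80% power at d=0.81 two-sided (0.71 one-sided). A non-significant between-arm result is inconclusive for effects of this size.

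3. If 0.518 proves to be another type of effect size, say so and give the power that matches it, with any correlation assumed.
4. Keep df=41 and t=1.683 only with an explanation of the calculation they came from. Otherwise correct them to the values for 25 + 25 (df=48; 1.677 one-sided or 2.011 two-sided).

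The cost is wording. The Protocol describes a recruitment period that ran to December 2024, so the 60 or 47 per arm are given for scale and are not a request to enrol more. No test changes. The price is a less favourable power statement.

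### The sample size rests on a one-sided 5% critical value whose degrees of freedom do not fit 25 per arm, while the analysis is set at p=0.05 with no side stated

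*SAP*

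**What the plan says.** The SAP states a significance level in two places.

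- **Sample Size, Randomization and Formation of Groups.** The aim is given as "In order to exceed the 80% power level", with 50 participants, 25 in each arm. The level, effect size and critical value are given together: "at a significance level was set at 5% with an effect size of 0.518 (df=41; t=1.683". The side is not stated in words.
- **Statistical Analyses.** "The significance level between the data was accepted as p=0.05". Again no side is given. The tests listed for that level begin with an unpaired t-test between the arms. For repeated measures the plan says "dependent sample t-test and mixed design ANOVA were used to compare repeated measurements between two independent groups". For non-normal data it says "Mann-Whitney U test was used to compare data not showing normal distribution", and for categories "Categorical variables were compared using chi-square test and Fisher's exact chi-square test". The Wilcoxon and Friedman tests are also listed.

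Neither document uses a term for one-sided or two-sided testing, and neither states a directional hypothesis. The Protocol's aim is worded neutrally: it is to assess what the training does to body composition, biochemical and clinical measures, and to sarcopenia.

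**The concern.** A critical value printed beside a significance level shows which test was used for sizing. Here it shows a one-sided test, and nothing in the analysis section says that the data will be tested that way. If the analysis is two-sided, as a reader would normally take an unqualified 0.05 to mean, the trial was sized against an easier threshold than the one it will face. The stated power then describes a different test from the one reported.

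The degrees of freedom raise a second doubt. They do not belong to a comparison of two arms of 25, so the printed figures do not describe the planned comparison even before the side is considered. At stake is whether the power claim can be relied on, and whether a reader can tell which threshold a borderline result should meet.

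**Working it through.** **Inputs.** From the SAP: level 5%, df=41, t=1.683, effect size 0.518, 25 per arm, power above 80%, analysis level p=0.05. The type of effect size (between-arm d, paired dz, or f) and its endpoint are not given, so all three readings are shown.

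**1. The printed critical value.**
- One-sided 5%: t(0.95; 41) = 1.6829, which rounds to the printed 1.683.
- Two-sided 5%: t(0.975; 41) = 2.0195.
- P(T > 1.683) on 41 df is 0.0500 in one tail and 0.1000 in two.

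The figure reproduces exactly as a one-sided 5% point, whatever 0.518 measures.

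**2. The degrees of freedom.** Two arms of 25 give 25 + 25 − 2 = 48. The critical values there are 1.677 one-sided and 2.011 two-sided. A df of 41 would fit 43 participants in two groups, or 42 pairs. With a paired effect of 0.518, a one-sided test with n=42 has 95.1% power, but the SAP states neither that n nor that power.

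**3. The side in the analysis section.** Mixed-design ANOVA, Friedman and chi-square tests have no direction. The t-tests, Mann-Whitney, Wilcoxon and Fisher tests can be run either way, and the SAP does not say which.

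**4. Power with 25 per arm at 5%** (exact noncentral t).

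| Reading of 0.518 | Noncentrality | One-sided | Two-sided |
|---|---|---|---|
| Between-arm d | 0.518 × √(25×25/50) = 1.831 | 56.4% | 43.4% |
| Paired dz, n=25 (df=24) | 0.518 × √25 = 2.59 | 80.8% | 70.0% |
| f, so d = 2 × 0.518 = 1.036 | 1.036 × √12.5 = 3.663 | 97.5% | 94.8% |

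For 80% power, the between-arm reading needs 47 per arm (94) one-sided or 60 per arm (120) two-sided. The paired reading needs 25 or 32. The f reading needs 13 or 16 per arm.

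**5. An observed effect equal to 0.518.**
- Between-arm d: the smallest significant difference is 1.677/√12.5 = 0.474 SD one-sided and 2.011/√12.5 = 0.569 SD two-sided. The value 0.518 lies between them: t=1.831, p=0.037 one-sided and 0.073 two-sided.
- Paired, n=25: t=2.59, two-sided p=0.016. Significant under either rule.
- f: t=3.66, two-sided p=0.0006. Significant under either rule.

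**The case against.** The strongest reply is that the SAP has only one analysis rule, p=0.05. The 1.683 is a planning input, and no passage tells an analyst to judge results against it. This stands, and it rules out two inferences that a reader might draw. One is that the favourable-direction false-positive rate doubles from 2.5% to 5%. The other is that the plan leaves harm untested. Both would follow only from a one-sided analysis, which the documents nowhere prescribe.

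A reader might also infer that an arm difference equal to the planned effect must pass under one rule and fail under the other. That is so only if 0.518 is a between-arm d. The SAP does not say so, and that reading does not reach the stated power on either side. Nor can all the planned tests be called non-directional; that is certain for three of them only.

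Finally, it can be said that the larger fault is a sample-size calculation that does not fit two arms of 25, with the one-sided value only a symptom. That is fair as to size. It does not dispose of the point, because the side has to be settled before any corrected power can be stated.

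**Conclusion.** The point holds as a mismatch between design and analysis. The printed critical value is certainly the one-sided 5% point, and its degrees of freedom certainly do not match 25 per arm. The analysis level has no stated side, and no directional hypothesis supports one-sided sizing. This is a design figure that needs correcting, not just a missing detail.

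The size of the effect depends on the undefined 0.518. Moving from one-sided to two-sided 5% costs 13 percentage points of power if it is a between-arm d (56.4 − 43.4), about 11 if it is a paired effect at n=25 (80.8 − 70.0), and about 3 if it is f (97.5 − 94.8). On the paired reading, the side alone decides whether the 80% claim is met. On the between-arm reading the claim fails either way. On the f reading it is met either way and the side matters little. These comparisons assume a two-sided analysis at 0.05, the conventional reading of the unqualified level but not one that the SAP confirms.

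**What to change.** In the SAP's Statistical Analyses section, state: *All tests are two-sided at a significance level of 0.05.*

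In the sample-size section:
- label t=1.683 (df=41) as the one-sided value used in the calculation already carried out, so that the record is kept;
- state what 0.518 measures and for which endpoint;
- give the two-sided critical value for the planned arm comparison (df=48; t=2.011);
- restate the power that 25 per arm delivers at two-sided 5%, in place of the present 80% claim.

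The last step is essential. Printing 2.011 beside an unchanged 80% claim would be false on the between-arm reading (43.4%) and on the paired n=25 reading (70.0%).

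The cost is wording only. The stated power becomes less favourable on every reading. No added patients are required, and naming the side does not by itself repair the sample size.
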